While in clinic, individuals will complete a tablet-based (iPad application) short screening questionnaire to assess study eligibility. The screening questionnaire captures self-reported phenotypic characteristics including natural hair color at age 18 [red (including reddish-brown), blond, dark (including light brown, medium brown, dark brown, gray, and black)]; skin reaction to first strong summer sun [burn and blister, burn without blister, mild burn followed by a tan, or no burning (including no sunburn and no tan, tan with no sunburn, and no change in skin color)]; skin reaction to prolonged exposure to summer sun (no tan, light tan, or medium to dark tan), eye color [blue or gray, green or hazel, or dark (including light brown, dark brown, and black)]; and freckling (extensive, moderate, mild, or none). See **Appendix** for screening survey.

The eligibility screening tool also will include a short series of questions that will elicit information on performance of skin examinations. We will capture information on timing (ever and within the past 12 months) and administration (self, partner, trained professional) of skin examinations. The screening tool also will elicit information about personal melanoma history.

Patients without a personal history of melanoma will be invited to take part in the study if they i) have not had a skin examination within the past year and ii) report having naturally brown or black hair at age 18 (hair color = dark) and at least two of the three following phenotypic traits: 1) skin reaction to first strong summer sun = mild burn followed by a tan or no burning; 2) skin reaction to prolonged exposure to summer sun = medium to dark tan; 3) freckling = mild or none. In contrast, persons reporting a full body skin examination (completed by self, partner, or trained professional) within the past year, natural red or blond (fair) hair at age 18, or dark (brown or black) hair with fewer than three of these traits will be thanked for their interest and excluded from further study.

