For our H/L population patients eligible for study participation will identify themselves as H/L, 18 years of age and older, able to read and speak either Spanish or English fluently; there will be no exclusions based on reported race. Individuals will be excluded from the study if they have had or completed a full skin examination over the past year, report a prior history of melanoma, report having more than one SCC, or report having more than one BCC.

After signing informed consent, a biologic sample (saliva) will be collected for the purpose of DNA extraction determination of *MC1R* genotypes. All participants who carry high risk *MC1R* genotypes and a proportion of those who carry low risk or no *MC1R* variants will be randomized to the control or intervention arm.

For our white, non-Hispanic population information on demographics and cutaneous pigmentation will be collected using a structured screening instrument. For our H/L population demographics and cutaneous pigmentation information will be collected at baseline. Information on personal sun protection behavior and skin examinations will be obtained via structured questionnaire instruments at baseline and at two follow-up times, 6 and 12 months for white, non-Hispanic population, 3 and 9 months for our H/L population. Information on potential mediators of effect will be collected at the two follow-up times using structured questionnaire instruments. The H/L intervention portion of the study is funded as a main project on Moffitt's U54 competitive renewal award for which the project timeline totals 3 years (instead of 5 years for our white, non-Hispanic population study funded under ACS). Because of the difference in the duration of the

study it was necessary to be flexible with the timing of our outcome measures; we selected 3 and 9 months follow-up for our H/L population instead of 6 and 12 months to assure two-post intervention measurement with the project timeline. Additional constructs capturing fatalism, familism and acculturation will be obtained for H/L population at baseline.

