Participants reporting sun-sensitive phenotypes.

Participants having had a skin examination within the past year.

Exclusion Criteria for our H/L population:

Children under the age of 18

Participant whose medical records or self-report indicate an ethnicity aside from Hispanic.

Participants having had a skin examination within the past year.

Participants with a personal history of melanoma and/or more personal history of more than one SCC and/or BCC.

Primary Outcome of the Study:

Primary outcomes will be measured using an adapted version of a published survey assessing measures of sun exposure and sun protection (Glanz et al. 2008) (see **Appendix**).

For Aims 1 and 2, the 14-item measure for adults (Section A) will be used. Section A is completed by the study participant and elicits responses about his/her own sun protection and skin examination behaviors including: average number of hours spent outside during weekdays and weekend days in the summer; number of red or painful sunburns during the past 12 months; frequency of sun protection behaviors when outside in the summer sun; frequency of intentional tanning; color of untanned skin; and skin examinations by a health professional or by the study participant him/herself or his/her partner.

For Aim 1, the primary outcome of interest is average number of hours spent in the sun per week between 10am – 4pm. This measure will be a weighted average of the first two questions on the survey asking about number of hours spent outside during the hours of 10 to 4 on weekdays (Section A, Q1) and on weekend days (Section A, Q2). We will tailor the timeframe of Q1 and Q2 given in Glanz et al. to fit our Aim and our timeline (Glanz et al. 2008). At baseline the timeframe will be “in the past 12 months”; and for our white, non-Hispanic population at the 6 and 12 month follow-up surveys and

at 3 and 9 month for our H/L population, the timeframe will be “in the past 6 months” for our white, non-Hispanic populations and “in the past 3 months” for our H/L population.

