Aim 1. We will use a linear GEE regression model with main effects for the intervention (standard risk and prevention plus genetic education versus standard risk and prevention education only), time, and the interaction terms between the intervention and time. The interaction term will be the main test of interest as it assesses average departure from the slope due to the intervention. We will include other covariates related to dropout or involving potential baseline imbalances between the intervention groups as appropriate, as well as month of completion of the questionnaires to account for seasonality.

We will perform analyses to test whether participants and eligible non-participants differ on basic demographic variables using cross-sectional logistic or linear regression models for binary or continuous factors, respectively. We will perform attrition analyses to determine whether participants and dropouts differ on key variables. We will include these factors in the above ITT model to see if they affect the results. A few randomly missing observations have only a slight impact on power and do not introduce bias. However, large numbers of non-randomly missing values can bias results.

We also will conduct mediator analyses to determine whether the effect of the intervention on prevention behaviors is explained by health beliefs or cancer distress. We will use a series of models to examine whether (a) the intervention is predictive of the mediator, (b) the mediator is predictive of prevention behaviors in a multivariable model controlling for the intervention, and (c) the addition of the mediator to a

multipredictor model for prevention behaviors attenuates the estimated coefficient for the intervention. To assess mediation effects, we will use the approaches by Imai et al., which are available through add-on packages to existing statistical software (such as R and STATA) (Imai et al. 2010, Imai et al. 2012). Similar to the method of Preacher and Hayes (Preacher et al. 2008), their methods employ bootstrapping to estimate mediating causal effects . These analyses will be used to estimate the direct effect of the intervention via pathways other than through the posited mediator, its indirect effect via the mediator, and the degree of mediation. This approach will allow us to quantify the effect of the intervention due to the potential mediator (if any), which can inform future interventions or prevention strategies.

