Aim 2. Hypothesis testing for the binary outcome of full-body examination (yes/no) will follow the general analytic outline used in Specific Aim 1. This outcome will be modeled using the logistic framework of the GEE approach (i.e. specifying a logit link function), which properly accounts for the induced correlation from the repeated measures on participants over time, to assess ITT differences. These ITT differences comparing the probability of skin examinations will be presented as odds ratios with corresponding 95% confidence intervals where models will include main effects for intervention (standard risk and prevention plus genetic education versus standard risk and prevention education only), time (0, 6, and 12 months), and interaction term between the intervention and time. The interaction term will be used to test for possible differences in effects over time in the two study arms as the main test of interest. In addition, the logistic GEE model will contain baseline covariates and variables related to study participation and/or attrition as appropriate.

Exploratory Aim 3. We will use the GEE Poisson or ordinal regression models as appropriate with main effects for the intervention, time, and interaction term between the intervention and time, and will adjust for date of study enrollment to account for seasonality. Specifically, we are interested in estimating the intervention's efficacy in reducing the average number of red or painful sunburns in children.

All statistical analyses will be conducted by a member of the Biostatistics Core under the direction supervision of [name].

Analyses among individuals with low-risk *MC1R* genotypes will be conducted in a similar fashion to those detailed above. Because we do not expect to see ITT differences in prevention behaviors comparing those who receive a risk and prevention education intervention that includes feedback of *MC1R* genotype to those who receive a risk and prevention education session that includes only standard information among the low-risk group, power analyses are omitted.

Pilot study Aim 1. The overall prevalence of *MC1R* genotypes will be calculated with corresponding 95% confidence intervals.

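### Aim 2's main test is arm-by-time with month 0 as an outcome, but eligibility fixes month 0 at no in both arms, so the test cannot be fitted or has almost no power

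*Combined protocol and SAP*

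**What the plan says.** In STATISTICS, Aim 2, the yes/no outcome is modelled by a logistic GEE with intervention, "time (0, 6, and 12 months), and interaction term between the intervention and time". The interaction is to test for possible "differences in effects over time in the two study arms as the main test of interest". The coding of time is not stated. Aim 2 follows the Aim 1 outline, where the interaction is chosen because "it assesses average departure from the slope due to the intervention", which points to linear time.

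Eligibility is set out elsewhere. Under RESEARCH PROCEDURES (Summary), white non-Hispanic patients are invited if they "have not had a skin examination within the past year", and examinations by the patient, a partner or a professional all count. H/L patients are excluded if they "have had or completed a full skin examination over the past year". The Exclusion Criteria list "Participants having had a skin examination within the past year" for both populations.

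Primary Outcome of the Study (Aim 2) defines the outcome as any examination by a clinician, oneself or a partner. The recall window is 12 months at baseline, then 6 months (white non-Hispanic) or 3 months (H/L) at follow-up. The same section describes the outcome as measured at the two follow-up visits. Study power, Aim 2 claims 80% power for a between-arm odds ratio.

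**The concern.** The screening question and the baseline outcome cover the same behaviour over the same 12 months. Everyone who passes screening should answer no at month 0 in both arms, so month 0 carries no information on the intervention. The plan nevertheless enters it as an outcome and tests change from it.

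This leaves three ways to run the test, and none asks whether the intervention raises examination rates with useful power. Categorical time gives a month-0 log-odds of minus infinity in each arm. Linear time fits a line through a fixed zero cell. Leaving month 0 out turns the interaction into a comparison of the 6-month effect with the 12-month effect. The trial could reach its planned effect and still report a null primary result, or the analyst could be forced to choose a new test after seeing the first one fail.

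**Working it through.** **Inputs from the plan.** 250 high-risk participants per arm; 20% attrition, so 250 × 0.8 = 200; placebo rate 20%; odds ratio 1.8; two-sided alpha 0.05. The intervention odds are 0.25 × 1.8 = 0.45, so the rate is 0.45/1.45 = 31.0%. The plan gives no within-person correlation for Aim 2 (0.1 is for Aim 1), so I assume a range.

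**1. The plan's own figure.** For a comparison of two proportions, power = Φ{[d√n − 1.96√(2p̄(1−p̄))] / √[p₁(1−p₁)+p₂(1−p₂)]}, with d = 0.1103 and p̄ = 0.2552.
- n = 250: (1.745 − 1.208)/0.612 = 0.877, power 81.0%.
- n = 200, one visit: (1.560 − 1.208)/0.612 = 0.576, power 71.8%.
- n = 200, two visits averaged, effective n = 400/(1+ρ): 92.9% at ρ = 0.1, 83.4% at 0.5, 81.0% at 0.6.

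The stated 80% is thus the power of a between-arm comparison. It is not the power of an interaction.

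**2. Categorical time.** The month-0 log-odds is log(0/200) in each arm, so neither the month-0 contrast nor any interaction measured from it is identified. A standard GEE routine may still print output: in trial fits the month-0 term was about −29 to −35, with standard errors of about 10,000 or more, or undefined.

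**3. Linear time, t = 0, 1, 2 (units of 6 months).** I solved Σ(pₜ − μₜ) = 0 and Σt(pₜ − μₜ) = 0 in each arm.
- Placebo (0, 0.20, 0.20): logit μ = −3.055 + 0.965t.
- Intervention (0, 0.310, 0.310): logit μ = −2.616 + 1.060t.
- The interaction is 1.060 − 0.965 = 0.095, against a true log odds ratio of ln 1.8 = 0.588. Most of the effect goes into the intercept (−2.616 + 3.055 = 0.439), which is not the named test.

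**4. Simulated power.** 200 per arm, month 0 all no, odds ratio 1.8 at both follow-ups, independence working correlation, robust standard errors. There were 2000 replicates, except 200 for categorical time at correlations 0.15, 0.50 and 0.75.

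| Test | Latent correlation 0.15 | 0.30 | 0.50 | 0.75 |
|---|---|---|---|---|
| Categorical interaction, fits converged | 0 | 0 | 0 | 0 |
| Linear-time interaction | 10% | 11% | 11% | 14% |
| Interaction, 6 vs 12 months only | 5% | 6% | 5% | 6% |
| Between-arm effect, both follow-ups | 94% | 91% | 89% | 83% |

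With all 250 per arm, the linear interaction reaches only 12% to 16%.

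**5. Lower rate per window.** The planned 20% is over 12 months, while each follow-up asks about 6. If 20% is split evenly, the rate per window is 1 − √0.8 = 10.6%. At correlation 0.30 the linear interaction has 6% power, the 6-vs-12 interaction 5% and the between-arm effect 75%. No categorical fit converged.

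**6. H/L population.** 200 high-risk per arm less 20% is 160. With odds ratio 1.95 and a 20% control rate at correlation 0.30, no categorical fit converged. The linear interaction has 10% to 11% power, the follow-up-only interaction 5% and the between-arm effect 91% to 94%.

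**7. Some yes answers at baseline (white non-Hispanic, 20% placebo rate).** Across the correlations tried, interaction power is about 5% to 9% (categorical) or 14% to 19% (linear) at 2% yes. At 5% yes it is about 17% to 30%, and at 10% about 30% to 48%, under either coding.

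**The case against.** Four points deserve weight.

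- **The right contrast is already in the plan.** Primary Outcome of the Study places the outcome at the follow-up visits, General approach frames the aim as a between-arm difference in proportions over follow-up, and the power sections use a between-arm odds ratio. This is correct, and it makes the Aim 2 paragraph the odd one out. But that paragraph names the model and the main test, and it lists month 0 explicitly.
- **Not every baseline answer will be no.** Screening refers in places to a full-body examination and elsewhere to any skin examination, and the baseline form may be completed after the visit. A few yes answers would let a categorical model converge (about 97% of runs at 2% yes). Power stays far below 80%, however, and a primary test should not depend on response inconsistency.
- **The figures assume a constant effect.** If the effect appears late (odds ratio 1.0 at 6 months, 1.8 at 12), the linear interaction has 55% power and the follow-up main effect 40%. With 1.3 then 1.8, the figures are 32% and 65%. The between-arm test is therefore not best under every pattern. The plan's power statement, though, gives one odds ratio and no late-onset pattern.
- **Failure and a null result are different consequences.** A separated model gives no valid test. The null result belongs to the linear and follow-up-only readings. Since the coding is unstated, either could occur.

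For H/L the point is partly inference, because the Aim 2 paragraph gives no H/L time points. The exclusion and the 12-month baseline window are the same.

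**Conclusion.** The concern holds, and the plan needs changing before analysis. As written, the Aim 2 primary test is either not estimable (categorical time) or has about 10% to 14% power (linear time), against the stated 80%. With follow-ups only, it has 5% to 6% power for a constant effect and answers a different question. The data themselves are adequate: the between-arm effect over the two follow-ups has 83% to 94% power with 200 completers per arm.

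These figures rest on a 20% placebo rate at each visit, a constant odds ratio of 1.8 and assumed latent correlations of 0.15 to 0.75. At the lower rate per window in step 5, the between-arm effect falls to 75%, slightly under target, but the interaction is at 5% to 6%. Yes answers from up to 10% of participants at baseline do not bring the interaction above about 48%.

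**What to change.** Rewrite the Aim 2 analysis paragraph for both populations:

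1. Take month 0 out of the outcome vector. Fit the logistic GEE to the two follow-ups only (6 and 12 months; 3 and 9 months for H/L), with time as a category.
2. Name the intervention effect, averaged over the two follow-ups and reported as an odds ratio with 95% confidence interval, as the primary test.
3. Keep intervention-by-follow-up-time as a secondary test of whether the effect lasts or develops. This also covers a late-emerging effect.
4. Optionally, adjust for lifetime history of any skin examination, which is already collected at screening in both populations.
5. Reconcile the paragraph with Primary Outcome of the Study and the power sections, and state the rate per recall window that the power assumes.

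The cost is wording in the statistics section. No new data, visits or participants are needed. The change should be dated before any outcome data are compared by arm, so that it cannot be read as a response to a failed model.

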- **Evaluate the impact of receipt of *MC1R* genotypes on skin awareness and examination.** Determine the efficacy of a risk and prevention education session, which includes feedback of inherited *MC1R* genotype and corresponding information about genetic risk, to increase skin examinations at both short term (6 months) and long term (12 months) follow-up for our white, non-Hispanic population; for our H/L population, follow-up will occur at 3 and 9 months.

The secondary objective of this project is to:

- **Evaluate the impact of receipt of *MC1R* genotype on sun protection behaviors in children of study participants.** Determine whether a risk and prevention education session, which includes feedback of inherited *MC1R* genotype and corresponding information about genetic risk, can decrease the number of sunburns at both short term (6 months) and long term (12 months) follow-up in the children of white, non-Hispanic study participants; for our H/L study participants, follow-up will occur at 3 and 9 months.
- **Explore the prevalence of *MC1R* genetic variants in Hispanics living in the Tampa Bay.** We hypothesize that non-synonymous variants at *MC1R* known to be high-risk in non-Hispanic white populations of European ancestry will be readily identified among Hispanics living in the Tampa Bay area, but will occur as lower prevalence.
- **Correlate the degree of European genetic ancestry with *MC1R* variation in this Hispanic population.** We will genotype germline DNA using Ancestry Informative Markers to determine percent European (African and Asian) ancestry and correlate genomic ancestry with genetic variation in *MC1R*. We hypothesize that the prevalence of non-synonymous variants at *MC1R* observed among Hispanics living in the Tampa Bay area will decrease as the proportion of non-European (i.e. African or Asian) genomic ancestry increases.

PROJECT DESCRIPTION

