For our white, non-Hispanic population we propose an intervention study to examine whether knowledge of *MC1R* genotype can lead to positive health behavior changes to reduce the risk of future development of melanoma among persons who otherwise are presumed to be at reduced melanoma risk. We posit that phenotypically low-risk individuals informed they carry *MC1R* variant(s) that place them into a high risk category will adopt melanoma risk reduction behaviors. To test this hypothesis we will randomize 1000 white, non-Hispanic patients – 500 of whom are considered at high risk and 500 of whom are considered at low risk based on *MC1R* genotyping, and all of whom report having phenotypic characteristics protective for melanoma – to receive standard risk and prevention information or to receive personalized risk and prevention information based on *MC1R* testing results. Preventive and early detection behaviors will be assessed at baseline and at 6 and 12 months post-randomization.

We also will recruit 75 to 100 individuals self-reporting Hispanic ethnicity from the USF Morsani Family Medicine clinic. Because the purpose of this secondary aim is to better understand the prevalence and distribution of *MC1R* variants in these participants, Hispanic participants will not be randomized into the intervention trial and will not complete either baseline or follow-up surveys. At this time *MC1R* genotype results will not be provided to these participants, follow up will not be required of Hispanic participants and no additional materials or questionnaires will be given to participants of this pilot study.

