Pilot study Aim 2. Genotyping quality control for each AIM will first be assessed using standard sample-level and SNP-level metrics. Using markers and among samples passing quality control, individual genetic ancestry will be estimated using Structure. Prevalence of genotypes within percentile categories of European ancestry determined from AIMS and within categories of self-reported sun-resistant phenotype characteristics (where available) will be determined. The precision of prevalence estimate may be limited for variants occurring at low frequency. The current study sample size is constrained by available pilot funding, but it is expected that estimates obtained in the current study will provide preliminary data supporting future melanoma research among Hispanic populations in the Tampa Bay area and Puerto Rico.

DATA COLLECTION

We will collect selected Protected Health Information (PHI), including but not limited to Name, Address, Age, MRN, and SSN, for the purpose of patient identification, tracking, and contact. After the conclusion of the study, any PHI solely used for patient identification and tracking (e.g. MRN and SSN) will be permanently deleted.

Data coordination and management will capitalize on existing experience and available infrastructures of the Moffitt Cancer Informatics Core (CIC) and Research Information Technology (RIT) division. In coordination with Drs. [name] and [name], the CIC and RIT will develop a data management system, including tablet-based applications, for storage of data and tracking of participant completion status. They will oversee creation of the web-based follow-up questionnaires and implement an automated messaging system triggered by individual patient trajectories through the project timeline. Reports will be generated by the CIC and RIT for review by the study team to assure timely completion of the study goals.

Data collection will be performed by research study investigators and staff.

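### Pilot Aim 2 hypothesises that MC1R variant prevalence falls with non-European ancestry, but the stated analysis is a table by percentile category with no trend estimate, test or confidence interval

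*Combined protocol and SAP*

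**What the plan says.** Under STUDY PURPOSE AND HYPOTHESIS, one secondary objective is to "correlate genomic ancestry with genetic variation in" MC1R among Hispanics in the Tampa Bay area. A direction is attached: the prevalence of non-synonymous variants "will decrease as the proportion of non-European (i.e. African or Asian) genomic ancestry increases".

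The matching analysis is in STATISTICS, Pilot study Aim 2. After genotyping quality control, "individual genetic ancestry will be estimated using Structure". The next step is to determine "Prevalence of genotypes within percentile categories of European ancestry determined from AIMS", and likewise prevalence within categories of self-reported sun-resistant phenotype. That is all the analysis text for this aim. It does not say how many categories there will be or where they are cut, and it names no correlation coefficient, trend test, regression model or confidence interval.

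On size, PROJECT DESCRIPTION says "We also will recruit 75 to 100 individuals self-reporting Hispanic ethnicity". Pilot study Aim 2 explains that "The current study sample size is constrained by available pilot funding" and adds one caveat: "The precision of prevalence estimate may be limited for variants occurring at low frequency". Pilot study Aim 1, by contrast, promises 95% confidence intervals for overall prevalence.

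**The concern.** The objective asks how prevalence changes with a continuous quantity and predicts the direction. The analysis returns one percentage per ancestry band and stops. A reader of the results would have to decide by looking whether the percentages fall. In bands of about 19 to 25 people, chance alone can hide a real gradient or produce an apparent one.

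Two things follow. First, the hypothesis has no prespecified answer: any slope or test would be chosen at analysis, along with the number of bands and their cut-points, possibly after the data have been seen. Second, the pilot is meant to supply preliminary data for later research in Hispanic populations. A slope with its interval serves that use better than several imprecise percentages.

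**Working it through.** **No figure to reproduce.** The documents give no power, precision or effect size for this aim. Sample size (75 to 100) is theirs. Prevalence, strength of trend, ancestry distribution and number of categories below are assumptions.

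**Step 1: what is promised and what is specified.**

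- Objective: correlate ancestry with MC1R variation. Hypothesis: a monotone decrease with non-European ancestry, which is the same as an increase with European ancestry, since the two shares sum to one.
- Analysis: prevalence by percentile band, with no estimate linking the bands.
- Available data: an individual ancestry estimate for each person. The Ancestry Informative Markers section says the markers estimate the proportion of ancestry, so a continuous value exists before any grouping.
- Elsewhere: the General approach section calls for two-sided tests of all hypotheses but names none for this aim.

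**Step 2: precision of one band.** Assume quartiles and 30% prevalence. The half-width is 1.96 × √(p(1−p)/n), with p(1−p) = 0.21.

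- N = 75, about 19 per quartile: 1.96 × √(0.21/19) = 20.6 points.
- N = 100, 25 per quartile: 1.96 × √(0.21/25) = 18.0 points.
- Whole sample, for comparison: 10.4 points at 75 and 9.0 at 100.

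Wilson intervals for prevalences of 20% to 50% give similar values: about 18 to 21 points in a quartile of 18, and 15 to 18 in a quartile of 25.

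**Step 3: what the table could show.** Compare top with bottom quartile, two-sided 5%, 80% power, using n = [1.96√(2p̄(1−p̄)) + 0.842√(p₁(1−p₁) + p₂(1−p₂))]² / (p₂−p₁)², where p̄ is the mean of p₁ and p₂. With p₁ = 20%:

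- n = 18 per quartile (N = 75): p₂ must reach about 65%.
- n = 25 per quartile (N = 100): p₂ must reach about 58%.

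Only a very steep gradient would be detected reliably in this way.

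**Step 4: what grouping costs.** Simulated power, two-sided 5% score tests, 10,000 replicates per scenario, European ancestry distributed Beta(4,2), odds ratio (OR) per SD of European ancestry:

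| N | Prevalence | OR per SD | Continuous | Ordered quartile trend | Unordered quartile chi-square (3 df) |
|---|---|---|---|---|---|
| 75 | 20% | 1.5 | 24.5% | 23.8% | 15.2% |
| 100 | 20% | 1.5 | 31.1% | 29.1% | 18.4% |
| 75 | 30% | 2.0 | 70.0% | 65.2% | 47.4% |
| 100 | 30% | 2.0 | 82.4% | 78.8% | 61.4% |
| 75 | 50% | 1.75 | 63.7% | 57.5% | 41.2% |

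Over all 18 scenarios (two sample sizes; prevalence 20%, 30%, 50%; OR 1.5, 1.75, 2.0), the loss against continuous ancestry is about 1 to 6 points for the ordered quartile trend and about 9 to 23 points for the unordered chi-square. With ancestry distributed Beta(4,3) instead, the first two rows give about 26% and 34% for the continuous analysis. At the weak end of these assumptions no analysis of 75 to 100 people has good power.

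**The case against.** Three points can fairly be made for the plan.

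**The plan does not exclude a test.** The objective speaks of correlating, and the General approach section says hypotheses are tested two-sided. A reader might infer that the hypothesis can never be tested under this plan. The documents do not support that: they leave the method unspecified, and a slope could be fitted at analysis from data already in hand. What stands is narrower: no test or trend estimate is specified.

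**Grouping costs little when order is kept.** A reader might infer that percentile categories throw away 20 or more points of power. That follows only if the bands are compared with an unordered test, and the plan names no such test, nor quartiles. Against an ordered trend test the loss is about 1 to 6 points. Most of the larger gap comes from ignoring the direction that the hypothesis itself states. This objection stands in full.

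**It is a pilot.** Its size is set by funding, its output is called preliminary, and PROJECT DESCRIPTION gives its purpose as understanding the prevalence and distribution of variants. Tabulation suits that purpose, and the limited scope keeps the point minor. But the protocol also chose to state a directional hypothesis, and its precision caveat covers rare variants, not the reading of a trend across small groups.

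**Conclusion.** The point holds as a gap between hypothesis and analysis. A directional trend is hypothesised, the stated method is a table by unspecified percentile bands, and nothing elsewhere in the documents supplies a trend estimate, test or interval for it. Followed as written, the analysis does not address its own hypothesis.

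The size is modest. Band-level half-widths of about 18 to 21 points assume quartiles and 30% prevalence. The power figures rest wholly on assumed prevalence, slope and ancestry distribution, and they do not show that grouping is seriously wasteful. Nor would a better model guarantee an answer: at 20% prevalence and an OR of 1.5 per SD, the continuous analysis has only about 25% to 34% power. Its gain is an interpretable estimate with honest uncertainty, fixed in advance.

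This is a minor improvement to a secondary aim. The pilot participants are not randomised, and neither primary outcome is affected.

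**What to change.** In Pilot study Aim 2, name as the main result a logistic regression of variant carriage (at least one non-synonymous MC1R variant, yes/no) on the continuous proportion of European ancestry. Report the slope or odds ratio with a two-sided 95% confidence interval, and state the unit (for example, per SD or per 10 percentage points of ancestry). The hypothesis corresponds to a positive slope on European ancestry. Keep the percentile table as description, and state the number of categories and the cut-points in advance. Say that the estimate may be imprecise at this sample size, so that a wide interval is not read as absence of a trend.

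The cost is one extra model on data already collected, with no change to recruitment or genotyping. The model assumes approximate linearity on the logit scale, and the percentile table gives a rough check of that.
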